The data collectors and supervisors will undergo a week-long training workshop in research ethics for fieldwork and research protocol including study methods, procedures and tools. This training will be provided by the Co-Is and PI. A training workshop for the local research team (including but not limited to project managers, data collectors, team leaders, local co-investigators, quality control officers, translators, transcribers, database developers, data entry clerks) will be conducted in local offices prior to data collection. Training content will include information on research ethics in the field, rights of human subjects during research, research methodology and protocol, sampling procedures, informed consent, data collection tools, interviewing techniques, and data management, security, and quality. The JHSPH IRB

Training will also include opportunities for practice using the study methods and the forms and tools in English as well as their local versions. Training on processes and logistics for field management, supervision, communication and documentation will be provided by the local contractor.

Team Leaders/Field Supervisors will be required to report to the head of their country office on a daily basis. The local office will maintain contact with the Jhpiego/headquarters and will provide research updates every 2 to 3 days while data collection is on-going. The local office will maintain contact with the PI on a weekly basis throughout the contract period for the local contractor.

4. If the PI will not personally be on-site throughout the data collection process, provide details about PI site visits, the supervision over consent and data collection, and the communication plan between the PI and study team.

The PI, [name], or the Global Study Manager, [name], plan to travel from Jhpiego/headquarters to local offices for the preparation of data collection, training of assessors, and the supervision of the initial data collection. They worked with the other members of the team to develop the protocol and tools. Locally, the co-investigators (and other staff members in the Jhpiego/local office) will manage all aspects of the data collection and entry.

The PI or the Global Study Manager will also visit the data collection sites to support start-up of data collection and ensure that correct procedures are being followed with fidelity to the research protocol. All study investigators schedule weekly calls with the project manager for the local contractor to discuss study progress and any issues that require problem solving. Additional conference calls will be held on an ad hoc basis to ensure that the protocol is followed and proper records are kept. They will also address questions or concerns that arise during the fieldwork and data entry process.

B. Recordkeeping:

Describe how you plan to ensure that the study team follows the protocol and properly records and stores study data collection forms, IRB regulatory correspondence, and other study documentation. For assistance, contact [contact].

All study staff will be instructed of the study protocol and the need to adhere to it. A Field Manual and Standard Operating Procedures will be developed that outline, among other guidelines, processes for recording and storing data. Algorithms will be created for research assistants and data managers to ensure that data is collected and stored in line with the protocol. All data collected will be linked to the corresponding data collector and manager in order to track records.

Data will be collected electronically with tablets and the data tools will have quality assurance measures designed into the platform such as skip patterns and illogical responses.

The PI and research team will monitor all IRB correspondence and study documentation during their team meetings/conference calls.

C. Safety Monitoring:

1. Describe how participant safety will be monitored as the study progresses, by whom, and how often. Will there be a medical monitor on site? If yes, who will serve in that role? **N/A**
2. If a Data Safety Monitoring Board (DSMB), or equivalent will be established, describe the following:
 - a. The DSMB membership, affiliation and expertise. **N/A**
 - b. The charge or charter to the DSMB. **N/A**

- c. Plans for providing DSMB reports to the IRB. N/A
- 4. Describe plans for interim analysis and stopping rules, if any. N/A

D. Reporting Unanticipated Problems/Adverse Events (AE's) to the IRB (all studies must complete this section):

Describe your plan for reporting to the IRB and (if applicable) to the sponsor. Include your plan for government-mandated reporting of abuse or illegal activity.

We do not anticipate that this study will result in AEs. However, if any unanticipated adverse event or problems occur, the interviewer will immediately report it to the Local Co-Investigator, and will provide a written statement describing the incident. The local investigator will report it to the study PI and the study PI will report it to the JHSPH IRB and the local IRBs, named below:

NOTE: The IRB does not require submission for all AEs, only those that are unanticipated, pose risk of harm to participants or others, and are related to the study.

E. Other IRBs/Ethics Review Boards:

If other IRBs will review the research, provide the name and contact information for each IRB/ethics review board and its Federal Wide Assurance, if it has one (available on OHRP's website at <http://www.hhs.gov/ohrp/assurances>).

Indonesia

National Institute of Health Research and Development
Address: [name]
[contact]

Kenya

KEMRI Scientific Ethics Review Committee
[name];
Telephone numbers: [name], [name], [name];
Email address: [contact]

F. Collaborations with non-JHSPH Institutions:

For studies that involve collaboration with non-JHSPH institutions, complete the chart below by describing the collaboration and the roles and responsibilities of each partner, including the JHSPH investigator. This information helps us determine what IRB oversight is required for each party. Complete the chart for all multi-collaborator studies.

Insert Name of Institutions in Partner column(s); add additional columns if necessary.

	JHSPH	Partner 1	Partner 2
Jhpiego	X		
University of Indonesia		X	

For the following, indicate “P” for “Primary”, “S” for “Secondary” (as appropriate to role and level of responsibility.) Add additional items if useful.

1.	Human subjects research ethics training for data collectors	P	S	
2.	Day to day management and supervision of data collection	P	S	
3.	Reporting unanticipated problems to the JHSPH IRB/Sponsor	P	S	
4.	Hiring/supervising people obtaining informed consent and/or collecting data	P		
5.	Execution of plan for data security/protection of participant data confidentiality, as described in the Data Security and Confidentiality Protections section above .	P	S	
6.	Biospecimen processing, storage, management, access, and/or making decisions about future use	N/A	N/A	

XI. Jhpiego Dissemination Plans

A. **Check the box if you intend to disseminate findings from this study broadly.** Broadly means sharing findings through posters, abstracts at conferences and publications in journals, beyond immediate stakeholders such as MOH and sponsors.

1. Provide a brief description of your dissemination plan (include if you plan to have a writing workshop). Are the prospective forums (national and international conferences)?

Our planned documentation and dissemination will be mapped to our study objectives, ensuring that all relevant technical findings are presented through global fora in a timely manner. Channels for this dissemination include: the PPFP Global Movement community; our network of field presence (including through the large-scale, USAID-funded, Jhpiego-led MCSP, which supports PPFP in 22 countries and is globally recognized for establishing PPFP as a critical component along the continuum of care for reproductive health); the recently launched FP2020's FP platform, which Jhpiego co-designed; the donor community; professional associations; and other implementing partners. We will use these platforms to present field implementation highlights of our interventions. From commencement of the study throughout implementation at relevant time points, and following a writing workshop at the conclusion of data collection, we will globally disseminate learnings through the provision of country spotlights, media and other resources. Key knowledge outputs, including reports of findings and technical materials, will additionally be shared on an ongoing basis with the global community through research articles, including in peer-reviewed journals offering timely publication opportunities such as “field action reports” that capture ongoing learnings for rapid dissemination. Knowledge will also be shared through monographs and conferences.

- a. For journal publication (list all possible journals of interest)

- Contraception
- Reproductive Health
- Studies in Family Planning
- International Family Planning Perspectives
- Reproductive Health Matters.
- Studies in Family Planning
- BMC Public Health
- Global Health: Science and Practice Journal

b. For posters, presentations and abstracts (list all potential conferences and events)

- International Conference on Family Planning
- FIGO
- ICM
- ICN

B. Check the box if you will be working in advocacy with government throughout the project

a. You will be disseminating findings to government for policy change?

XII. Please complete the attached worksheet of your Logic Model and submit to Jhpiego IRBhelp with your completed research protocol. *This is for Jhpiego internal review only.*

COMPLETE THE FOLLOWING SECTIONS WHEN RELEVANT TO YOUR STUDY:

XIII. Secondary Data Analysis of Existing Data:

A. Study Design:

1. Describe your study design and methods. The study design must relate to your stated aims/objectives.

In addition to the methods described above, the study will monitor immediate postpregnancy family planning clients and participating providers and facilities through analysis of routine program and facility records. These records are outlined below.

FP Facility Register	Facility clients	Determine overall facility PPFP acceptance, PPFP method mix and adverse events	Monthly service statistic record review	Descriptive statistics
Supportive Supervision Records	Kenya: Intervention Site Providers Indonesia: All providers	Measure service quality against PPFP performance standards	Intervention Area: Kenya: 3 and 12 months post-training Indonesia: Beginning of the study, Year 2, Year 3 Control Area: Kenya and Indonesia: month 30	Descriptive, chi-sq, ANOVA (depending on sample size)

Family Planning Facility Registers: Information about immediate PPFP clients will be documented in a Family Planning register at the intervention and control health facility where they receive care – part of the health system. This information will be used to track overall PPFP service statistics, assist with validating responses from the Client Interviews, and help the study team ensure that the Client Interview sample continues to be representative of the overall client population (especially regarding adolescent enrollment).

Supportive Supervision Records: The project will employ Jhpiego staff and a ministry of health representative or consultant to provide Supportive Supervision to intervention facility providers trained in implant service provision and counseling at project facilities. Supportive Supervision is a proven method for improving the quality of services offered by trained providers through guiding, helping, and encouraging staff to continue using the skills they learn through training. Regular Supportive Supervision visits will be conducted to each facility. During these visits, supervisors use a Supportive Supervision Checklist to monitor the quality of services provided. Quality will be measured against a set of performance standards developed at the national level with stakeholders from each country. The study team will use

Supportive Supervision Records to track whether or not services are improving at project facilities. Data will be linked to facilities to assess overall facility quality and help determine the impact of the intervention.

2. Provide an estimated sample size and an explanation for that number.

Family Planning Facility Registers: We estimate that roughly 15% of women who deliver at intervention facilities and 10% of women who deliver at control facilities will accept a method of postpartum family planning and that on average 30 women per month will deliver in each of the 62 project facilities over the course of the project. Therefore, we anticipate facilities will collect information about approximately 3,906 postpartum FP acceptor clients during the 30 months of the study. Furthermore, we estimate that approximately 50% of women receiving postabortion care at both intervention and control facilities will accept a method of postabortion family planning and that on average 12 women per month will receive PAC at the project facilities over the course of the project. Therefore, we anticipate facilities will collect information about approximately 4,680 postabortion FP acceptor clients during the 30 months of the study. Based on these estimates, we expect to collect de-identified service statistics for approximately **8,586 postpregnancy FP acceptor clients**.

Supportive Supervision Records: Supportive Supervision will be provided to relevant health care providers at all participating facilities as part of the project's main activities. We anticipate that this will include around 5 providers per facility, for 200 providers in Kenya and 100 providers in Indonesia from both intervention and control facilities. This leads to supportive supervision records for review for around **300 total providers**.

3. Provide a brief data analysis plan and a description of variables to be derived.

Family Planning Facility Registers: Using FP Facility Register data, the study team will assess trends in service delivery at participating facilities including the total number of ANC clients, the total number of Labor and Delivery clients, total number of postabortion clients, the total number of postpartum family planning acceptors broken into the type of family planning method accepted. Additionally, the study and project teams will monitor facility records for reports of adverse events related to PPFP acceptance.

Supportive Supervision Records: Supportive Supervision Records will primarily be used to measure changes in service provision quality according to data collected during the Supportive Supervision. Overall changes in the number/percent of standards met will be calculated through difference in difference analysis. Facility aggregate provider performance information may also be calculated into assessment of facility readiness and overall facility quality.

B. Participants:

1. Describe the subjects who provided the original data and the population from which they were drawn.

Family Planning Facility Registers: Information about family planning service provision will be collected from all project facilities. All information recorded through facility records will be included in the sample. The sample will likely include the same women contacted during the client interviews. However, it may also include data on those who were otherwise ineligible for recruitment.

Supportive Supervision Records: Providers trained in PPFP counseling and method service provision as well as leadership and management working at study intervention facilities will be monitored using supportive supervision. All trained providers receiving supportive supervision will be included. It is probable that providers receiving supportive supervision will also participate in the structured interview.

2. If you are receiving, accessing, or using data from a U.S. health care provider, the need for HIPAA review is likely. If you plan to bring identifiable health information from a foreign country to a U.S. covered entity (e.g., lab at the Hopkins SOM), HIPAA may be triggered. If either of these conditions is met, check "yes" to the HIPAA question in the PHIRST application. **N/A**
3. If you plan to analyze human specimens or genetic/genomic data, provide details about the source of those specimens and whether they were collected using an informed consent document. If yes, explain whether your proposed use is "consistent with" the scope of the original consent, if it potentially introduces new analyses beyond the scope of the original consent, and/or if it introduces new sensitive topics (HIV/STDs, mental health, addiction) or cultural/community issues that may be controversial. **N/A**
4. Explain whether (and how) you plan to return results to the participants either individually or as a group.

Results will not be returned to the participants. However, project staff will use Supportive Supervision records to monitor provider performance and make adjustments to individual and/or group trainings and other follow-up activities as needed.

XVI. Data Coordinating Center:

Complete if JHSPH serves as the Data Coordinating Center.

A. How will the study procedures be developed?

The planned study procedures, including Study SOPs and the study Data Collector's manual, have been developed by the Jhpiego Baltimore Family Planning Team in concordance with the study teams in Kenya and Indonesia. The study teams in Kenya and Indonesia, as well as the study team in Baltimore, include research and technical experts, whose inputs and reviews ensure that their procedures are culturally, ethically, and technically appropriate.

B. How will the study documents that require IRB approval at each local site be developed? Will there be some sort of steering or equivalent committee that will provide central review and approval of study documents, or will template consent forms, recruitment materials, data collection forms, etc. be developed by and provided to the local sites by the coordinating center without external review?

All study documents, including all study tools, consent forms and recruitment materials are developed by the Jhpiego Baltimore Family Planning Team in concordance with the study teams in Kenya and Indonesia. While the Baltimore study manager oversees the process of study tool review, each study tool has been edited by key study research and technical staff in Baltimore, Kenya, and Indonesia to ensure research, technical and cultural relevance.

C. Will each local clinical site have its own IRB with an FWA? State whether the coordinating center will collect IRB approvals and renewals from the clinical centers; if not, explain why.

The study will gain approval from the Kenya Medical Research Institute (KEMRI) IRB in Kenya and the Kementerian Kesehatan (KemKes [Ministry of Health]) IRB in Indonesia. Local and JHSPH ethics approvals will be shared, along with letters of support from local ministries of health, with each local PI.

D. How will the coordinating center provide each local site with the most recent version of the protocol and other study documents? What will be the process for requesting that these updates be approved by local clinical center IRBs?

The Baltimore-based coordinating center keeps the most up-to-date versions of all study tools and the study protocol in a dropbox folder shared by the Kenya and Indonesia based PIs and researchers. The study manager monitors the

dropbox folder to ensure the integrity of the forms and keeps back-up copies of the tools in the event anything happens to the tools in the dropbox. All up-to-date quantitative data collection tools will similarly be stored in the REDCap system which will be used to physically collect the data. Any changes to the study tools must be made in accordance with the PPFP Choices “Study Tool Alteration and Data Steward Management” SOP, which states that all suggested edits to tools will only be made by the Data Steward, who is the Baltimore-based study manager, or her chosen deputy, after conversation with the study staff member who suggests the edit and, when necessary, a secondary reviewer (member of study staff) and the PI.

Any alterations to the study tools or protocol that would require IRB approval will be immediately sent to the relevant IRBs as an amendment. These will be sent to the Kenya and Indonesia IRBs by the in-country PI, and to the JHSPH IRB by the PPFP Choices PI or study manager. The study team will await approval from all necessary IRBs prior to enacting the proposed amendments.

E. What is the plan for collecting data, managing the data, and protecting the data at the coordinating center?

All quantitative data will be collected through the secure web application, REDCap, and transmitted via a secured network to the central database which, for Jhpiego, is located in the Jhpiego Nairobi office. All equipment used to enter or access study data will be password protected and will have security software installed. In addition, each REDCap user will be required to log-in using their personal ID to enter or access the data. Only the database administrators will have the permission to download the data from the central database. When data is exported for statistical analysis, it will be de-identified and kept in a password protected directory accessible to the statistician and the data managers.

All qualitative data obtained during FGDs, KIIs, and IDIs will be collected via audiotapes at the interview. The audiotapes will be transcribed and the transcriptions will be stored in a password protected database with security software installed. While the audiotapes are being transcribed, they will be stored in a locked cabinet. As soon as the transcription is completed and saved, the audio files will be destroyed. When data is exported for statistical analysis, it will be de-identified and kept in a password protected directory accessible to the statistician and the data managers.

F. What is the process for reporting and evaluating protocol events and deviations from the local sites?

Who has overall responsibility for overseeing subject safety: the investigators at the recruitment site, the Coordinating Center, the Steering Committee, or a Data and Safety Monitoring Board (DSMB)? Is there a DSMB that will evaluate these reports and provide summaries of safety information to all the reviewing IRBs, including the coordinating center IRB? Please note that if there is a DSMB for the overall study, then the coordinating center PI does not have to report to the coordinating center IRB each individual adverse event/problem event that is submitted by the local site PIs.

If any unanticipated adverse event or protocol deviations occur, the data collector or study staff will immediately report it to the Local PI, and will provide a written statement describing the incident. The local PI will report it to the study PI and the study PI will report it to the JHSPH IRB and the local KEMRI and/or KemKes IRBs in accordance with Jhpiego’s IRB policy and SOP for Reporting of Adverse Events and Serious Adverse Events for Jhpiego Studies. Overall responsibility for overseeing subject safety lies with the Coordinating Center, which will regularly monitor study progress and will be in regular communication with the in-country staff

G. Some FDA regulated studies have different AE reporting criteria than that required by the IRB (IRB Policy No. 103.06). How will you reconcile the different requirements, and who is responsible for this reconciliation?

n/a

H. Who is responsible for compliance with the study protocol and procedures and how will the compliance of the local sites be monitored and reviewed? How will issues with compliance be remedied?

Overall responsibility for compliance with the study protocol and procedures lies with the PI and the Study Manager. Compliance of the local sites will be the responsibility of the local PIs who will report to the Study PI. Compliance will be monitored from the Baltimore location through biweekly calls between the Baltimore Study staff, occasional site visits, and through monitoring of data quality. Compliance will be monitored by the Kenya and Indonesia PIs through the weekly communication with and monthly reports from the data collection teams, regular site visits, and regular data monitoring, quality assurance and verification.

REFERENCES

[1] World Health Organization. (2012). Family planning: a health and development issue, a key intervention for the survival of women and children. Retrieved on October 10 2013, from WHO:
http://www.who.int/reproductivehealth/publications/family_planning/rhr_12_23/en/index.html

[2] World Health Organization. (2005). Report of a WHO Technical Consultation on Birth Spacing
http://www.who.int/maternal_child_adolescent/documents/birth_spacing.pdf

[3] Moore, Z. (2013). Family Planning Needs During the Extended Postpartum Period in Kenya. USAID

[4] FP2020. (2015). *Indonesia*. Retrieved September 19, 2015, from FP2020:
<http://www.familyplanning2020.org/entities/59>

[5] Indonesia Demographic Health Survey, 2012

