Key Informant interviews, Focus Group Discussions and In-Depth Interviews: *Data analysis:* Key informant interviews, Focus Group Discussions and In-Depth Interviews will all be analyzed using Grounded Theory methods. Initial KII, FGD and IDI responses will be translated, transcribed, coded, and analyzed using software to facilitate data management. Quality of translation will be checked for each (KII, FGDs and IDIs) through back translation of a randomly-selected subset of 6 interviews. Using analytical software, coding will be used to conceptually name the data and reduce it to manageable units of information that cover broad and general categories. *A priori* codes will be developed based on the concepts of interest in this research (perception of risk, benefits and beliefs, etc.) and the study aims. As additional KII, FGDs and IDIs are conducted, these *a priori* codes will be complemented by additional codes that reflect themes and concepts that emerge from the data. Codebooks will be developed for the different concepts to facilitate consistency in the coding process. The coded data will be organized into a hierarchy of themes which are then meaningfully linked to each other to show patterns, relationships and explanations. In conjunction with the coding process, memos will be used

to develop conceptual categories and themes and to track emerging insights and interpretations [11]. Qualitative research software such as QSR NVivo or ATLAS.ti will be used to analyze the data.

Client Interviews: Data Analysis: After data have been thoroughly cleaned, the study team will report on all outcomes included in the study tools as well as the service statistics collected as part of this study (see Section XI). The team will calculate the proportion of pregnant/postpartum women who choose a FP method during antenatal care (ANC) or early labor, and, of those, what proportion received the FP method in the immediate postpregnancy period (prior to discharge). Regression models may be used to explore differences in acceptance of PPFP between the intervention and control facilities, different demographic groups, or to compare acceptance among clients receiving varying levels of care (as determined through facility and performance assessments). Select data from the client interviews will be combined with key facility level indicators for a multilevel analysis of the factors affecting intention to use and receipt of PPFP.

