- B. **Key Informant interviews, Focus Group Discussions and In-Depth Interviews:** Data will all be analyzed using **Grounded Theory methods**. Initial KII, FGD and IDI responses will be translated, transcribed, coded, and analyzed using software to facilitate data management. Quality of translation will be checked for each (KIIs, FGDs and IDIs) through back translation of a randomly-selected subset of 6 interviews. Using Atlas.TI analytical software, coding will be used to conceptually name the data and reduce it to manageable units of information that cover broad and general categories. A priori codes will be developed based on the concepts of interest in this research (perception of risk, benefits and beliefs, etc.) and the study aims. As additional KIIs, FGDs and IDIs are conducted, these a priori codes will be complemented by additional codes that reflect themes and concepts that emerge from the data. Codebooks will be developed for the different concepts to facilitate consistency in the coding process. The coded data will be organized into a hierarchy of themes which are then meaningfully linked to each other to show patterns, relationships and explanations. In conjunction with the coding process, memos will be used to develop conceptual categories and themes and to track emerging insights and interpretations].
- C. **Family Planning Facility Registers:** Using FP Facility Register data, the study team will assess trends in service delivery at participating facilities including the total number of ANC clients, the total number of Labor and Delivery clients, total number of postabortion clients, the total number of postpartum family planning acceptors broken into the type of family planning method accepted. Additionally, the study and project teams will monitor facility records for reports of adverse events related to PPFP acceptance.
- D. **Supportive Supervision Records:** Supportive Supervision Records will primarily be used to measure changes in service provision quality according to data collected during the Supportive Supervision. Overall changes in the number/percent of standards met will be calculated through difference in difference analysis. Facility aggregate provider performance information may also be calculated into assessment of facility readiness and overall facility quality.

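### The supervision checklist used to help judge impact is scored by the coaching team at its own visits, and the planned rounds cannot remove any resulting rater bias

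*Protocol*

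**What the plan says.** **Who coaches.** Protocol XIII.A.1: "The project will employ Jhpiego staff and a ministry of health representative or consultant to provide Supportive Supervision to intervention facility providers". The same paragraph presents this as an improvement activity: "Supportive Supervision is a proven method for improving the quality of services offered by trained providers". Appendix II lists it under Indonesian intervention-site preparation and under intervention continuation activities.

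**Who scores, and when.** "During these visits, supervisors use a Supportive Supervision Checklist to monitor the quality of services provided". The yardstick is external to the project: "Quality will be measured against a set of performance standards developed at the national level with stakeholders from each country".

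**What the score is for.** "Data will be linked to facilities to assess overall facility quality and help determine the impact of the intervention". SAP D: "Supportive Supervision Records will primarily be used to measure changes in service provision quality". The analysis is given in Protocol XIII.A.3 and repeated in SAP D: "Overall changes in the number/percent of standards met will be calculated through difference in difference analysis". Both add that aggregated provider performance may feed into facility readiness and quality.

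**When scores are taken** (table in XIII.A.1). Kenya intervention area: 3 and 12 months after training. Indonesia intervention area: start of study, Year 2 and Year 3. Control areas in both countries: month 30 only.

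**What is not said.** No non-coaching rater, second rater or agreement check is described. The staff-blinding item (V.C.5.F) is answered as not applicable. The scorer of the control areas is not named.

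**The concern.** The people whose job is to raise performance against the standards also record whether the standards were met, at the visits where they do that work. They know the arm, and they have an interest in seeing improvement. If they mark borderline items generously in facilities they have coached, the score rises without any change in practice.

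At stake is the reading of the service-quality result. A gain in standards met at intervention sites could be real improvement, generous scoring or both, and the records would not tell them apart. The score may also become a facility-quality variable in the multilevel analysis, which serves the primary research question on service-delivery and provider determinants.

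**Working it through.** The plan gives no figure for this score, so there is none to reproduce. The check asks what the planned rounds can and cannot remove.

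**1. Model.** Write an observed score as Y = T + b, where T is true standards met and b is rater leniency. I and C are the intervention and control areas; 1 and 2 are an earlier and a later round.

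- Single-round contrast: Y_I − Y_C = (T_I − T_C) + (b_I − b_C).
- Difference in difference: bias = (b_I2 − b_I1) − (b_C2 − b_C1).

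**2. Consequences.**

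- Same leniency in both arms: single-round bias = 0.
- Leniency constant over rounds within each arm: difference-in-difference bias = 0.
- Leniency b on the intervention side only: single-round bias = +b.
- Leniency that grows at later intervention rounds only: difference-in-difference bias = + the growth.

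**3. Are the four scores available?**

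- Kenya: the first intervention score comes 3 months after training, so there is no pre-training score. Control has month 30 only.
- Indonesia: intervention has a score at study start and later ones. Control has month 30 only.

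Y_C1 is missing in both countries, and Kenya also lacks a pre-training Y_I1. The difference in difference cannot be formed as described, so its ability to cancel constant leniency is lost. What remains is a single-round contrast, which carries b_I − b_C in full, or a within-arm change in the intervention area, which carries any drift in leniency and has no control counterpart.

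**4. Is b_I likely to differ from b_C?** Under V.C.5.A, control facilities get the interventions only in the last six months, after data collection; Appendix II puts this in months 31–36. On that schedule the month-30 control score is taken at uncoached sites, whoever takes it, while intervention scores follow coaching. XIII.A.2 points the other way, describing supervision at all participating facilities. The texts do not agree on coverage:

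- XIII.A.1 text and XIII.B.1: intervention facilities.
- XIII.A.1 table: Kenya intervention providers only, Indonesia all providers, yet a month-30 control round in both countries.
- XIII.A.2: all participating facilities, with 200 + 100 = 300 providers from both arms.

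**5. Illustration of size (assumed values only).** The checklist length is not given. With 20 to 30 items, one lenient mark adds 1/30 = 3.3 to 1/20 = 5 points, and two add 2/30 = 6.7 to 2/20 = 10 points.

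Take no true effect, leniency b on the intervention side only, SD 15 points, 5 providers per facility, ICC 0 to 0.5, and a single-round comparison at two-sided 5%. The chance of a significant result favoring the program is Φ(b/SE − 1.96), with SE = 15 × √(2/n_eff) and n_eff = n/(1 + 4 × ICC). Two values of n per arm, each assuming an even split: 300/2 = 150 (XIII.A.2), and 26 facilities (III.B) × 5 / 2 = 65.

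- b = 5, n = 150, ICC 0: SE = 1.73, Φ(2.89 − 1.96) = 82%.
- b = 5, n = 150, ICC 0.5: n_eff = 50, SE = 3.0, Φ(1.67 − 1.96) = 39%.
- b = 5, n = 65: 19% to 48%.
- b = 10: 92% to 100% with n = 150, and 59% to 97% with n = 65.

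More providers do not dilute a systematic difference; they make a false signal more likely.

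**The case against.** Much can be said for the plan. Scoring is against nationally developed standards, and a ministry representative or consultant takes part, which limits discretion. The protocol does not say that each facility has a fixed coach, nor who scores the controls; the same supervisors may score both arms, and shared leniency would cancel. The records are routine program data, while the study is sized on six-month LARC+PM acceptance from client interviews administered by research assistants. Coaching toward the checklist is no bias in itself, since meeting more standards is the intended effect.

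All of this stands, and it rules out several stronger readings that a reader might infer:

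- That the intervention side is self-rated. Providers do not score themselves; the implementing team scores them.
- That the contrast is known to be biased. The direction is plausible, but no document shows leniency or its growth over visits.
- That no analysis could ever remove the bias. Constant or shared leniency would cancel in a suitable design; it is the planned rounds that do not allow this.
- That the error certainly enters the determinants model. The wording is permissive, and neither V.C.4 nor SAP E names the supervision records.

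The risk itself is not answered. National standards still require a judgment on each item, and scorers common to both arms would still be rating coached sites in one arm and, on the V.C.5.A schedule, uncoached sites in the other. The facility audits by research assistants (V.C.1) cover records, staffing, reported training and commodities; no checklist of observed service quality is described, so they cannot stand in for this score.

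**Conclusion.** The concern holds as a risk of detection bias in a secondary measure. Followed as written, the plan has the implementing team score service quality at its own coaching visits, uses that score as evidence of impact, and schedules rounds from which rater leniency cannot be separated. The bias probably favors the program, but its size is unknown. The 3.3 to 10 points and the false-positive chances above show sensitivity under assumed checklist length, SD, ICC and one-sided leniency; they do not estimate what will happen.

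A reader might infer that the trial's main comparison is compromised. The documents do not support that: six-month LARC+PM acceptance comes from client interviews and is not affected. Damage is confined to the service-quality result and, if the score is used there, the facility-quality term in the multilevel model.

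**What to change.** For every round whose score enters the analysis:

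- complete and lock the checklist before any feedback at that visit;
- use the same scorers in intervention and control areas;
- where feasible, use supervisors from the existing pool who have not coached that facility;
- record a scorer code with each score.

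Where this is not feasible, report coach-made scores as program monitoring only, keep them out of the multilevel model, and do not present them as impact evidence.

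In the protocol, state who scores the control areas, and reconcile the XIII.A.1 table and text, XIII.A.2 and XIII.B.1 on which facilities are supervised.

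The cost is a few lines in the field procedures and SAP D, plus some extra travel and scheduling. The size of the supervisor pool is not stated, so the swap may not be possible everywhere; the monitoring-only rule covers that case. Two limits remain. Swapped supervisors still belong to the implementing team and know the arm, so the risk is reduced but not removed. The missing earlier scores are not restored either, so SAP D should not claim a difference in difference that the scheduled rounds cannot supply.
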